Motor adaptation refers to behavioural changes induced by new environmental dynamics, commonly studied by inducing an unfamiliar perturbation into an otherwise familiar task. Here, split-belt speed manipulations will be used **to study implicit motor adaptation**, i.e. without raising conscious attention to the adaptive behaviour nor demanding an explicit strategy [18]. Motor adaptation plays an important role in **the acquisition (early) phase of motor learning**, the hallmark of which is reaching a stable level of performance. In contrast, the late consolidation phase of motor learning is characterized by: 1) **automatization**, or the ability to withstand dual task interference; 2) **transfer**, or the ability to generalize to untrained circumstances and 3) **retention**, or the ability to sustain improvements after a period without practice. [20]. Our previous work has shown that despite disease-related damage, **patients with PD can still reconfigure neural networks** to optimize motor control and achieve partially consolidated motor learning gains [21]. Interestingly, from recent study on manual tasks, it appears that **variable practice** (random versus blocked) and practice requiring greater adaptation (with versus without contextual interference) led to **worse immediate performance but better learning retention** in PD and older adults. This strongly suggests that in order to enhance better storage in motor memory and automatic retrieval of practice gains, **practice conditions are critical**. In this project, we want to study these phenomena for the first time during gait. More specifically, we want to know how PD impacts upon maintenance of stride amplitude when adapting to varying split-belt conditions in order to achieve robust learning.

Research Questions and Hypothesis

We aim to investigate two research questions:

We intend to better understand the impact of PD on the **adaptive response to different split-belt conditions** relative to healthy age-matched controls.

We will investigate the short-term effects of different split-belt conditions in order to determine the **optimal conditions for long-term training** in patients with FOG and test which condition leads to the best 24-hour retention.

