We hypothesize that being exposed to larger contrasts between split-belt speeds (ratio) will result in improved gait symmetry and better savings in motor memory, thus leading to better retention effects and this more so in controls than in PD. We also hypothesize that variable split-belt conditions (changing ratios) will lead to better adaptive capacity to transitions than steady split-belt walking with a consistent ratio.

V. Methodology of the research

Number of participants: This pilot study investigating the short-term effects of split-belt walking on gait asymmetry and motor learning is conducted in collaboration with CAUK and will include a total number of 128 participants i.e 64 at each centre comprising 32 patients with PD and 32 healthy controls.

Recruitment: Older adults will be recruited from an existing database of healthy volunteers. Recruitment of PD patients will be conducted via a database of patients that has been built up over the years in our laboratory in collaboration with the neurologist at the Movement Disorders clinic at UZ Leuven ([name]. [name]). Flyers containing study information will be handed to people expressing interest to participate.

Inclusion and Exclusion Criteria: PD patients with FOG who can walk at least 5 minutes at a stretch will be included in this study. Exclusion criteria are: participation in treadmill training in the 3 months prior to the study, other neurological impairments, orthopedic injuries that could influence gait or balance, cardiovascular exercise risk factors, dementia or self-reported DBS-related postural or gait disturbances.

Design: Patients will be tested in the ON phase of medication on consecutive days in a session of about 2 hours. Figure 2 shows that the included subjects will be randomized into 4 treatment groups to compare the impact of different (3:4 and 1:2) and changing ratios of split-belt walking relative to traditional treadmill training (Tied-Belt). Effects will be analysed pre-post (I-II) and after 24 hours (III) retention. The second training session (III-IV) will explore the possible benefits of repeated training and serves as a pilot for a larger training study.

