Outcome Measures

Laboratory FOG assessment: A FOG ratio score will be calculated [24]. FOG will be analysed with accelerometer sensors (APDM) during FOG provoking tasks (360° turning in place (right/left side alternating) for 1 minute with and without a cognitive dual task.

Overground gait analysis: the following gait variables will be analysed during 5 trials of 5m gait with comfortable pace (assessed via accelerometer sensors (APDM) and Vicon/Qualisys motion capture analysis): step length, gait asymmetry, gait variability, bilateral coordination [25] and gait velocity.

Treadmill gait analysis: adaptive capacity during transitions will be assessed by analysing the above mentioned variables during changing split-belt conditions. Retroreflective markers will be placed bilaterally on the limbs to allow gait analysis at 100Hz with infrared cameras.

Descriptors: MDS-Unified Parkinson's Disease Rating Scale (MDS-UPDRS) [26], New Freezing of Gait Questionnaire [27], Mini Mental State Exam (MMSE) [28], Montreal Cognitive Assessment (MoCA) [29], Frontal Assessment Battery, Falls Efficacy Scale International (FES-I), Mini-BESTest [30], Borg Rating of Perceived Exertion, Visual Analogue Scale for fatigue and number of falls during the last 6 months.

VI. Planned Statistical analysis & Data Management

Data storage: Part of the data obtained on paper (e.g. questionnaires, informed consent forms) will be stored in an excel file. The data obtained by computerized measures will all be stored in the original digital files, and the main variables will be stored in excel datafiles. All data will regularly be backed up to a secure KU Leuven server.

Statistics: Data from both centres will be pooled for the statistical analysis. The immediate effects and short term (24 hour) retention of split-belt treadmill training on overground gait symmetry and the freezing ratio during the turning task are the **main outcomes of interest**. Repeated measures ANOVA with group and training condition as between subjects factors will be employed in order to test this. Effect sizes will be determined and a post-hoc power calculation will be performed to ascertain sample sizes for a planned larger training study.

VII. Safety

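### The four main results have no lead, and the repeated measures ANOVA is unbiased but less precise than comparing the randomised arms with adjustment for the value at I

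*Protocol*

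**What the plan says.** The Statistics paragraph of section VI names as main outcomes "The immediate effects and short term (24 hour) retention of split-belt treadmill training on overground gait symmetry and the freezing ratio" during the turning task. Two measures, each assessed immediately and at 24 hours, give four results; none is ranked first. On the test it says "Repeated measures ANOVA with group and training condition as between subjects factors will be employed in order to test this". It names no baseline covariate and does not list the within-subject levels. It adds: "Effect sizes will be determined and a post-hoc power calculation will be performed to ascertain sample sizes for a planned larger training study".

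Section V (Design) gives the time structure, "Effects will be analysed pre-post (I-II) and after 24 hours (III) retention", and the purpose of randomising, "to compare the impact of different (3:4 and 1:2) and changing ratios of split-belt walking relative to traditional treadmill training". The sample is "64 at each centre comprising 32 patients with PD and 32 healthy controls", at two centres.

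The second research question in section IV seeks the best conditions for long-term training "in patients with FOG and test which condition leads to the best 24-hour retention". The hypothesis there is that "being exposed to larger contrasts between split-belt speeds (ratio) will result in improved gait symmetry" and better retention, more so in controls than in PD.

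**The concern.** Two things are at stake.

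- **Precision.** The four arms are randomised, and every participant is measured at I before training. A repeated measures comparison of I with III subtracts the whole baseline value, although only the fraction rho of it predicts the value at III. An ANCOVA subtracts just that fraction. With few patients per arm the difference can be material, and it costs no data.
- **Which result counts.** Section IV asks about 24-hour retention in patients with FOG, and section VI uses the effect sizes to plan a larger study. With four unranked results, the protocol does not say which one answers the question or which effect size is carried forward.

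**Working it through.** **Inputs from the protocol.** Two centres x (32 PD + 32 controls) = 128, which reproduces the stated total. There are four arms, so 64 PD / 4 = 16 PD per arm.

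**Assumptions, because the protocol gives no figures.** Equal allocation; equal SD at I and III (unit SD); no dropout; two-sided alpha 0.05; correlation rho between I and III from 0.3 to 0.9.

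**Step 1: variance of an arm comparison at III.**
- Repeated measures on I and III (a comparison of changes): 2(1 - rho).
- ANCOVA of III on I: 1 - rho^2 = (1 - rho)(1 + rho).
- Ratio, ANCOVA to change: (1 + rho)/2.

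**Step 2: 95% CI half-width for one arm minus tied-belt, PD only.** The formula is t x sqrt(variance) x sqrt(2/16), with t = 2.00 (60 df for change, 59 df for ANCOVA). At rho 0.5:
- Change: 2.00 x sqrt(1.00) x 0.354 = 0.71 SD.
- ANCOVA: 2.00 x sqrt(0.75) x 0.354 = 0.61 SD.

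| rho | variance ratio | saving | half-width, change | half-width, ANCOVA | equivalent n per arm, 16/ratio |
|---|---|---|---|---|---|
| 0.3 | 0.65 | 35% | 0.84 | 0.67 | 24.6 |
| 0.5 | 0.75 | 25% | 0.71 | 0.61 | 21.3 |
| 0.7 | 0.85 | 15% | 0.55 | 0.51 | 18.8 |
| 0.8 | 0.90 | 10% | 0.45 | 0.42 | 17.8 |
| 0.9 | 0.95 | 5% | 0.32 | 0.31 | 16.8 |

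**Step 3: power of the 3-df test at III under assumed effects.** Take tied-belt 0, 3:4 0.4, 1:2 0.8 and changing 0.6 SD, fully kept at 24 hours. The mean is 0.45 and the sum of squared deviations is 0.2025 + 0.0025 + 0.1225 + 0.0225 = 0.35. The noncentrality is n x 0.35 / variance, with n = 16 for PD alone, or n = 32 for PD plus controls if controls respond alike. At rho 0.5 in PD this is 5.6/1.00 = 5.60 for change and 5.6/0.75 = 7.47 for ANCOVA.

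| rho | PD only: I-III repeated measures | PD only: ANCOVA | PD + controls: I-III repeated measures | PD + controls: ANCOVA |
|---|---|---|---|---|
| 0.3 | 34% | 50% | 64% | 84% |
| 0.5 | 46% | 59% | 80% | 91% |
| 0.7 | 70% | 77% | 96% | 98% |
| 0.8 | 87% | 91% | above 99% | above 99% |
| 0.9 | above 99% | above 99% | above 99% | above 99% |

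Within either population ANCOVA is at least as powerful. The gain shrinks as rho rises.

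**Step 4: is the planned test biased?** No. With no true effect and 16 per arm, simulation gave the condition-by-time test rejection rates of about 4% to 6% at rho 0.3 to 0.8. The ANCOVA gave 4.4% to 4.9%.

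**Step 5: four unranked tests.** If independent and each at 0.05, the chance of at least one false positive is 1 - 0.95^4 = 18.5%. Simulation with time correlation 0.5 and between-measure correlation 0 to 0.7 gave about 16% to 18%.

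**The case against.** Six counter-arguments deserve an answer.

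- **Baseline is already used.** A reader might infer that the plan ignores baseline or is biased. The documents do not support this. Section V makes I the reference for the effects, so condition by time compares changes from I. What remains is a difference in precision between two valid analyses.
- **Retention can be tested.** A reader might infer that the planned model cannot separate a retained effect from a lost one. That would hold for a single condition-by-time term over I, II and III with no follow-up. Section V names I-II and III separately, so that reading is the less natural one, and an I-III comparison does address retention.
- **PD-only is not the planned test.** This stands. The plan uses all 128 participants. If controls respond like PD, the planned I-III test has 80% power at rho 0.5, against 59% for a PD-only ANCOVA. The two answer different questions, however, and on the same participants ANCOVA still gains (91% against 80%).
- **False-positive rate.** The 16-18.5% figure tempts a claim of uncontrolled error. The protocol calls the study a pilot and states no alpha or success rule. The figure applies only if any single positive result were read as confirmatory.
- **SAP content.** Covariates and contrasts are often left to a SAP, which is not shown here. But the protocol itself fixes the model and lists the main outcomes, so both can be judged as written.
- **Choice of lead.** Section IV lists PD versus controls first, and the freezing ratio is also a main outcome. Choosing the lead is therefore partly a judgement, though the second research question and the study title support it.

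**Conclusion.** The point holds as one of precision and clarity, not validity. The planned comparison is unbiased, but its variance exceeds what a baseline-adjusted comparison of the randomised arms would give. Adjustment saves 35% at correlation 0.3, 25% at 0.5 and 15% at 0.7, and little at 0.8 to 0.9. At correlation 0.5 it is worth about 21 rather than 16 PD patients per arm. The protocol gives no correlation, allocation ratio, alpha or effect size, so the size of the gain is conditional on the assumptions shown; its direction is not in doubt over that range.

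The missing lead is plain from the text. It matters even in a pilot, because one effect size has to be carried into the larger study. The baseline-adjusted comparison is the main recommendation and the choice of lead is secondary. The change should be made; confidence in its practical size is medium.

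**What to change.** Amend the Statistics paragraph of section VI as follows:

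1. Compare the four randomised arms at III, and likewise at II, by ANCOVA adjusted for the value at I. Report each split-belt arm's difference from tied-belt in PD patients with its 95% CI. The overall 3-df test alone does not show which arm is best. Differences between split-belt arms can be reported in the same way and, with equal allocation, have the same half-width.
2. Keep the repeated measures ANOVA with group and condition for the PD-versus-control question, without baseline adjustment, because those groups are not randomised. State its within-subject levels.
3. Name 24-hour overground gait asymmetry in PD as the lead outcome, with one fixed asymmetry measure and retention defined as III adjusted for I. This is the net 24-hour effect, not the loss from II to III. Use its effect size to plan the larger study.

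**Cost.** The change is to wording only and needs no extra data. The freezing ratio and the immediate effects rank lower. A PD-only lead test has less power than the planned PD-plus-control test if controls respond alike (59% against 80% at correlation 0.5 under the assumed effects). If only half the assumed effect remains at 24 hours, neither PD-only analysis has useful power at that correlation (14% for I-III repeated measures, 17% for ANCOVA), so the intervals will carry more information than the test.

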Split-belt treadmill walking, whereby the walking speed of each leg can be manipulated independently, is a useful tool to study both motor switching and modulating gait asymmetry. In a recent study at our lab, motor switching ability during different asymmetric split-belt conditions was studied in patients with and without FOG. It was shown that non-freezers were **able to adapt spatial gait symmetry** to different switching split-belt conditions similarly as healthy controls. However, **adaptive capacity was reduced in freezers** (figure 1A) [18]. The powerfulness of the split-belt paradigm was also confirmed by the fact that immediately after the switch, FOG was evoked in two cases. In another study from the group at Christian-Albrechts University Kiel (CAUK), Germany, the **short-term effects of 10 minutes split-belt walking** were studied through reducing the belt velocity of either the body side with the longer or shorter step length in PD. **Gait asymmetry, bilateral coordination and the consecutive reduction in step lengths were improved** in the tied-belt condition after subjects walked with reduced velocity at the side with the longer step length ("better side reduction") (figure 1B) [19]. These exciting pilot results provide **proof-of-principle evidence** for the current project. To consolidate these findings, our research group in collaboration with the group at Kiel will undertake two studies, probing short term motor adaptation (present study) and prolonged motor learning (future study) to alleviate freezing-related gait deficits.

[figure not shown]

Figure 1. A) Impaired adaptive capacity of patients with PD with FOG during split-belt gait (data from KUL: mod. according to Mohammadi et al. 2015); B) Step length during baseline, early and late split-belt adaptation (25% reduced belt's speed of the leg with the longer step length (best-side reduction)) and after effect (data from CAUK: mod. according to Fasano et al. 2016).

IV. Study objectives

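### The group × training-condition ANOVA has no stated term for the condition effect in patients with FOG, which the second research question needs

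*Protocol*

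**What the plan says.** Section IV (Research Questions and Hypothesis) sets two questions. The first is how PD changes the adaptive response "relative to healthy age-matched controls". The second is to find the best conditions for long-term training "in patients with FOG and test which condition leads to the best 24-hour retention". The accompanying hypothesis expects larger belt-speed contrasts to improve symmetry and savings, "thus leading to better retention effects and this more so in controls than in PD".

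Section V plans 128 participants, 64 with PD and 64 controls over two centres, randomized to four training conditions. Freezing is the entry criterion for patients: "PD patients with FOG who can walk at least 5 minutes at a stretch will be included in this study".

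Section VI (Statistics) pools the centres and says that immediate and 24-hour effects on "overground gait symmetry and the freezing ratio during the turning task are the" main outcomes. The only analysis it names is: "Repeated measures ANOVA with group and training condition as between subjects factors will be employed in order to test this". It continues: "Effect sizes will be determined and a post-hoc power calculation will be performed to ascertain sample sizes for a planned larger training study". Section III describes that later work as "prolonged motor learning (future study) to alleviate freezing-related gait deficits".

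**The concern.** Section V also calls the four training arms groups. Because the ANOVA has training condition as its own factor, its group factor can only be PD versus control. With time as the repeated factor, two terms of this model carry information on training condition:

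- **Condition × time** asks whether the conditions differ on average over patients and healthy controls.
- **Group × condition × time** asks whether the condition differences are larger in one population than in the other. That is the right test for the first question and for the hypothesis about controls and PD.

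The second question asks something else: how the conditions compare in patients with FOG. Neither term is that quantity by definition. A reader who takes condition × time as the answer gets a diluted patient effect on the freezing ratio if controls have little freezing to reduce. On gait symmetry, where the protocol itself expects controls to retain more, the same reader could credit patients with an effect carried by controls. The pilot is meant to choose a training condition for patients and to supply effect sizes for a larger study, so the quantity reported matters.

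**Working it through.** **Inputs from the protocol.** 2 × (32 + 32) = 128 participants, which reproduces the stated total. With two populations and four conditions, 128 / (2 × 4) = 16 per cell. Equal allocation is assumed, as no ratio is given.

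**Assumed inputs.** The protocol gives no SD, effect size or alpha. I use change scores, patient SD 1, control SD *r*, patient contrast *d* between two conditions, control contrast *c* × *d*, and two-sided 5%.

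**What each term estimates**

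- Within-PD contrast: *d*, SE = √(2/16).
- Condition × time: *d*(1 + *c*)/2, SE = √((1 + *r*²)/32).
- Group × condition × time: *d*(1 − *c*), SE = √((1 + *r*²)/8).

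*Freezing ratio, controls unchanged (c = 0).* Condition × time gives *d*/2. For example, patient effects against tied-belt of 0.5, 1.0 and 0.75 in arms A, B and C appear as 0.25, 0.5 and 0.375. The interaction equals the patient effect only because *c* is exactly zero. If controls respond just as patients do (*c* = 1), it has no signal and rejects in 5% of trials, however much the conditions differ in patients.

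*Gait symmetry, controls respond more.* At *c* = 1.5, (1 + 1.5)/2 = 1.25. At *c* = 2, (1 + 2)/2 = 1.5. The average overstates the patient effect by those factors. If only controls respond (by about 1 SD, *r* = 1), condition × time is significant in about 52% of trials with no effect in patients.

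**Power for the freezing ratio with controls unchanged.** Take *d* = 1.007, which gives the within-PD test 80%: 1.007/√(2/16) = 2.848 on 60 df. Signal-to-noise relative to that test is (1 + *c*)/√(1 + *r*²) for condition × time and (1 − *c*)/√(1 + *r*²) for the interaction. At *c* = 0 the two are equal.

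| r | relative signal-to-noise | power of either stated term |
|---|---|---|
| 0.25 | 0.97 | about 78% |
| 0.5 | 0.89 | about 71% |
| 0.75 | 0.80 | about 62% |
| 1 | 0.71 | about 52% |

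At *r* = 1, for instance, condition × time has 0.5035/√(2/32) = 2.014 on 120 df, hence 52%.

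**Controls respond partly (r = 1).** The averaged term matches the within-PD test when 1 + *c* = √2, so *c* = 0.41. Its power at *c* = 0.25, 0.41 and 0.5 is 70%, 80% and 85%, while it estimates 0.63, 0.71 and 0.75 of the patient effect.

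**Type I error.** When neither population has a condition effect, simulation of the stated terms gave 4.9% to 5.4% for *r* from 0.25 to 1.25.

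**The case against.** The strongest reply is that the sentence names a model and its factors, not which term answers which question. A two-factor model with time contains the simple effect of condition within PD, and details of contrasts and error terms are commonly left to a statistical analysis plan. It is true that a within-PD comparison is compatible with the sentence. But the protocol fixes this ANOVA as the test of its main outcomes, and the terms it yields as they stand answer a different question from the one that is to select the patients' training condition.

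A second reply is that the retention clause of the second question has no population limit of its own, and that the hypothesis explicitly compares retention in controls and PD. That also stands: the interaction term serves a stated aim and should stay. It still does not tell the sponsor which condition works best in patients.

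A third reply concerns power. Controls at a floor would probably also vary little, so the realistic rows of the table are the low values of *r*, where 71% to 78% compares with 80%. This is a fair correction. The 52% figure pairs controls who have no freezing to reduce with a freezing ratio that varies as much as in patients. When controls respond more than about 0.41 times as much as patients at equal SDs, the averaged term has more power, though for another quantity.

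A fourth reply is that the protocol does not say whether controls do the turning task. If they do not, there is no group factor for the freezing ratio and the comparison reduces to one within patients. The dilution then disappears, but the sentence still needs to say so.

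A reader might also infer that the planned tests have inflated type I error, or that the later study will be wrongly sized. The document supports neither. The stated terms hold their level, and the protocol prescribes neither patient contrasts on a shared error term nor an effect size from a shared SD or from the averaged term. Those are risks only if someone chose to work that way.

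**Conclusion.** The point holds as a mismatch between the stated test and the second research question, and it is worth fixing. That neither term is the patient effect follows from the model and needs no assumed effect size. The size does rest on assumptions: half the patient effect on the freezing ratio if controls do not change, and 1.25 to 1.5 times the patient effect on gait symmetry if controls respond 1.5 to 2 times as much. The direction on gait symmetry follows the protocol's own hypothesis about retention, but its amount is assumed.

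Loss of power is the secondary issue. It ranges from 2 to 28 percentage points for *r* from 0.25 to 1 with controls unchanged, and it is probably at the small end if controls are at a floor. The joint ANOVA is not wrong in itself. It suits the first question and the patient-control hypothesis.

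**What to change.** Keep the joint ANOVA, state that it tests the first question and the PD-versus-control hypothesis, and add:

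> *Question 2 is answered for both main outcomes by the training condition × time effect within the PD patients, estimated with the PD residual variance. Effect sizes for the larger training study are PD condition differences divided by the PD SD.*

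Control freezing-ratio values, if collected, can still enter the joint model and need not be limited to description. If controls do not do the turning task, say so and apply only the within-PD analysis to that outcome.

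The change is wording only, with no new data and no change of outcome. The within-PD analysis has about 60 instead of 120 error df, so the critical t is 2.000 instead of 1.980 and intervals are about 1% wider. It also gives up the extra power that averaging would bring if controls respond much as patients do.

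### For the randomised comparison of training conditions, the named repeated-measures ANOVA is valid but less precise than adjusting for the assessment I value already collected

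*Protocol*

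**What the plan says.** Section VI of the protocol (Statistics) names as main outcomes "The immediate effects and short term (24 hour) retention of split-belt treadmill training on overground gait symmetry and the freezing ratio during the turning task". The test is then fixed in one sentence: "Repeated measures ANOVA with group and training condition as between subjects factors will be employed in order to test this". Group here is Parkinson's disease (PD) versus healthy control (HC); training condition is one of the four treadmill regimens in Table 1. No covariate is named, and the protocol nowhere mentions baseline adjustment. The same paragraph adds: "Data from both centres will be pooled for the statistical analysis".

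The Design paragraph of section V says that "the included subjects will be randomized into 4 treatment groups" and defines the effects: "Effects will be analysed pre-post (I-II) and after 24 hours (III) retention". Assessment I is therefore measured before training on every participant. Section V also gives the size: the study "will include a total number of 128 participants i.e 64 at each centre comprising 32 patients with PD and 32 healthy controls".

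The hypothesis adds a difference in response between the groups, "thus leading to better retention effects and this more so in controls than in PD".

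**The concern.** With effects defined as I to II and I to III, the natural reading is that assessment I is a level of the repeated factor. The condition-by-time contrast for a pair of assessments is then a comparison of change scores. A change score fixes the slope on baseline at 1, whereas a covariate lets the data estimate it. Under randomisation both estimate the same condition effect, and the covariate version has the smaller variance unless the correlation is close to 1.

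The 64 patients are spread over four conditions. One of the two research questions is which condition is best for patients with freezing of gait, so the within-patient contrasts matter and each rests on few people. The resulting effect sizes are also meant to set the sample size of a larger training study, so imprecision here carries into that design.

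The point is about precision only, and only for the randomised factor. PD versus HC is not randomised, and change from baseline is defensible there.

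**Working it through.** **Head count.** 2 centres × (32 PD + 32 HC) = 128, which agrees with the protocol. It states no prospective alpha, power, effect size or SD, so there is no power calculation to reproduce.

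**Inputs from the protocol.** 64 patients, 64 controls, four conditions, assessments I, II and III.

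**Assumptions.** Equal allocation (64/4 = 16 per condition in each group); equal variance at each assessment (SD = 1); two-sided 5%; 80% power; r = 0.5, 0.7 or 0.9.

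**Variance per participant.**
- Change from I: 2(1 − r)
- Adjusted for I: 1 − r² = (1 − r)(1 + r)
- Ratio, adjusted to change: (1 + r)/2 = 0.75, 0.85, 0.95
- Extra participants needed by the change analysis, 2/(1 + r) − 1: 33%, 18%, 5%

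**One split-belt arm versus tied-belt within PD, fitted in the 128-person model.**
- Change: SE = √[2(1 − r) × 2/16], error df = 128 − 8 = 120.
- Adjusted: SE = √[(1 − r²)(1 + 1/58) × 2/16]. The factor 1 + 1/58 is the cost of estimating the slope within patients (64 − 4 − 2 = 58). Error df = 120 − 3 = 117, for two baseline slopes and one centre term.
- At r = 0.5: change SE = √(1.00 × 0.125) = 0.354; adjusted SE = √(0.75 × 1.0172 × 0.125) = 0.309.

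Noncentral-t results, change → adjusted:

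| r | Detectable difference (SD), 5% | Same, Bonferroni over 3 contrasts | Power for 0.8 SD, uncorrected |
|---|---|---|---|
| 0.5 | 1.00 → 0.87 | 1.16 → 1.01 | 61% → 73% |
| 0.7 | 0.77 → 0.72 | 0.90 → 0.83 | 83% → 88% |
| 0.9 | 0.45 → 0.44 | 0.52 → 0.51 | no gain |

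A patients-only model agrees within 0.01 SD.

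**Simulation** (6000 runs; 2 groups × 4 conditions × 2 centres × 8 people; 1 SD baseline gap between PD and HC). The SE of the 1:2 versus tied-belt contrast in PD was 0.353 for change against 0.308 adjusted (r = 0.5), 0.273 against 0.254 (0.7), and 0.158 against 0.155 (0.9). Null rejection was about 5% for both. A separate simulation of 3000 runs per scenario found both estimators unbiased.

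**Centre.** A constant centre offset of 0.8 SD cancels in the change score (SE stays 0.353), so omitting centre costs the stated analysis nothing. In the adjusted model, omitting it raises the SE from 0.308 to 0.315 (r = 0.5) and from 0.254 to 0.257 (r = 0.7).

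**PD versus HC.** With the same true change in both groups and a 1 SD baseline gap, the adjusted model produces a spurious group difference of (1 − r) × 1 SD = 0.50, 0.30 and 0.10 SD, with rejection in 82%, 55% and 21% of runs against 5% for change. The adjusted model must therefore not be used for that comparison.

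**The case against.** The best case for the plan is that nothing in it is wrong. The analysis is valid, one model serves both research questions, and the study calls itself a pilot. The size of the loss depends on a correlation the protocol does not give. Gait is averaged over five trials and repeated the same day and a day later, so r could be high and the gain negligible. Covariates are often settled in a SAP, which may exist. For the pooled condition contrast (32 per condition), the absolute gain in power is also smaller: at r = 0.5, power for 0.8 SD goes from 89% to 95%, and the detectable difference from 0.71 to 0.62 SD. Finally, the change leaves two models where there was one, with a rule on which answers which question.

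Much of this stands as a limit on size. The gain does depend on r and nearly vanishes at 0.9, and the statement that only large differences are detectable fits r of about 0.5 to 0.7 only. It does not remove the point. The protocol names the model and its factors for its main outcomes, so this is a choice it makes and not a detail it leaves open. The relative variance gain is the same for the pooled contrast, and the patient contrasts are the ones that bear on choosing a condition for patients.

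**Conclusion.** The concern holds, as a loss of precision and not as bias or error. For the randomised conditions, the stated analysis has 1.33, 1.18 and 1.05 times the variance of a baseline-adjusted one at r = 0.5, 0.7 and 0.9. The benefit of adjusting is moderate at 0.5 to 0.7 and negligible at 0.9. This rests on an assumed r, equal variances, equal allocation, and the reading that assessment I is a level of the time factor. It is a change the sponsor should make, with medium confidence in how much it will yield. It does not extend to PD versus HC.

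**What to change.** In section VI, Statistics, specify for the training-condition effects at II and at III a baseline-adjusted model: ANCOVA at each assessment, or one mixed model for both. Its terms are the assessment I value, training condition, group, group by condition, baseline by group, and centre as a fixed factor. Estimate each split-belt arm against tied-belt within PD and within HC, and use group by condition for the hypothesis of a larger effect in controls.

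Keep the repeated-measures analysis of change from baseline for the overall PD versus HC comparison, and say explicitly that this comparison is not to be read from the adjusted model.

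The cost is wording, a statement of which analysis answers which question, and about three error degrees of freedom (120 to 117). No added assessment or participant is needed.
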